3.2 Primary Study Endpoints

The quality of bone that is generated: bone vitality, % of residual bone graft material, % of inflammatory tissue, if any.

3.3 Secondary Study Endpoints

We will be checking for bone volume stability through CBCT analysis comparing it from the time of placement, 8 months post-grafting and one-year post implant insertion.

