Objectives.	The purpose of this study is to evaluate the influence of bone allograft particle size on bone vitality and bone volume in subjects undergoing sinus augmentation for the placement of dental implants.
Methodology	Randomized, split mouth
Study Duration	42 months
Participant Duration	24 months
Population	10 subjects, male or female, healthy
Study Sites	NYU College of Dentistry- clinic 5 W
Number of participants	10 participants expected to be enrolled

CONFIDENTIAL

This material is the property of the NYU College of Dentistry. Do not disclose or use except as authorized in writing by the study sponsor

Study Summary

Title	A RANDOMIZED, SPLIT MOUTH STUDY OF THE EFFECTS OF BONE GRAFT PARTICLE SIZE ON BONE VITALITY AND BONE VOLUME OUTCOMES IN SUBJECTS UNDERGOING SINUS AUGMENTATION FOR THE PLACEMENT OF DENTAL IMPLANTS
Short Title	Bone graft particle size on bone vitality and volume
Protocol Number	19-00996
Phase	Phase 2
Methodology	Randomized, single-masked, split-mouth, single center study
Study Duration	3.5 years
Study Center(s)	Single-center
Objectives	To determine the effects of small and large bone graft particles vs large particles alone on percent vital bone, percent residual graft material, measured histologically from bone biopsies of the grafted site taken at the time of dental implant placement from subjects undergoing sinus augmentation for the placement of dental implants. Dental radiographs taken post operatively will be used to estimate bone graft volume differences between conditions.
Number of Subjects	10
Diagnosis and Main Inclusion Criteria	Subjects have missing upper back teeth on both the left and right sides and insufficient bone height (<5mm) for dental implant placement
Study Product, Dose, Route, Regimen	Bone graft material will consist of four to six grams of commercially available human donor bone allograft (Puros Allograft Bone Particles, Zimmer Biomet, Warsaw, IN USA) consisting of cortical and cancellous bone chips of either 250-1000 microns, and 1000-2000 microns size, vs. 1000-2000 microns size alone.
Duration of administration	Bone graft material is implanted, dental implants are placed, restored and subjects are followed for a period of two years after implants are restored

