1.1 Background

Tooth loss due to dental caries, and periodontal disease is a major cause of chewing dysfunction among adults in the United States. Dental implants have been approved for use in the United States for tooth replacement since 1983. Root form dental implants are made of titanium or titanium alloy that allows for the phenomena called osseointegration to occur. Osseointegration is the biological process by which bone cells adhere and grow onto the root form titanium implant. The process of osseointegration takes from 4-8 weeks, after which a dental prosthesis can be placed on the implants. This prosthesis can be a crown, or a bridge, or a denture. Dental implants can be placed anywhere in the mouth where teeth were formerly present, however the quality and quantity of jaw bone determines whether a dental implant may be placed.

The upper jaw can be a challenging area for implant placement. The upper jaw bone or maxilla, is generally less dense than other part of the mouth. Further, after tooth loss, the upper jaw undergoes a process called residual ridge resorption, that is, in the absence of teeth, mechanical load on the jaw is lessened, and bone atrophy occurs. Concurrently, the maxillary sinus, which is adjacent to the upper jaw bone, undergoes a process call pneumatization, whereby the sinus space increases, and the amount of maxillary jaw bone present diminishes. The amount of bone loss due to these processes is variable. When the amount of available jaw bone in the maxilla is less than 6 millimeters, (the length of the shortest commercially available dental implant) the placement of dental implants is not feasible without bone augmentation.

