The purpose of this study therefore is to compare the new bone formation and bone graft volume between bone graft mixes comparing two different size graft particles and follow the survival of the dental implants up to two years after prosthetic loading.

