There will be 3 CBCT scans. The first scan is a pre-operative diagnostic and is standard of care. The second scan is taken right after the sinus augmentation procedure and is for research purposes. When the contralateral sinus is performed at the same visit then there will be one CBCT scan for both sinuses. In the case where the contralateral sinus will be performed at a consequent visit then another limited field of view (FOV) CBCT will be performed. The third scan is performed 8 months after the sinus augmentation surgery as per standard of care prior to implant placement for evaluation and pre-surgical planning.

There is very little risk associated with dental x-rays. The risk involved is exposure to a very low dose of radiation. Routine safety techniques will be used including the placement of a lead apron and a thyroid collar to protect a subject from radiation. Periapical radiographs of the implant site will be taken using a bite plane/paralleling device preoperatively, intraoperatively and at the follow up visits. These periapical radiographs are standard implant evaluation procedures.

CONFIDENTIAL

This material is the property of the NYU College of Dentistry. Do not disclose or use except as authorized in writing by the study sponsor

A CBCT will take place at visit 1 as a standard preoperative evaluation procedure. The CT scan will be used to assess the sinus quality, amount of crestal bone and the presence of arterioles in the lateral wall of the sinus. A CBCT will be taken immediately after the procedure to assess the integrity of the graft placement and establish the height achieved. This will help us compare with the third CBCT which will be taken at 8 months mark about the volume changes and loss of height due to graft shrinkage.

The CBCT scan used for both sides maxillary scans is 80x80 mm FOV, The kVp is 90 and mA is 5. The CTDI number for this field of view and exposure is 6.61mGy. For one side maxillary scans, 60x60 mm FOV with CTDI number of 5.74mGy.

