6.11 Follow up visit 8 (18 month \pm 7 days)

- Review medical and dental history, and concomitant medications
- Record blood pressure and pulse
- Oral examination
- Record adverse events as reported by participant or observed by investigator (Research purposes)
- Standardized peri-apical radiographs, if needed
- Oral photographs

6.12 Final study visit 9 (24 month \pm 7 days) End of study assessments

- Review medical and dental history, and concomitant medications
- Record blood pressure and pulse
- Oral examination
- Record adverse events as reported by participant or observed by investigator (Research purposes)
- Provide any final instructions to participant
- Standardized peri-apical radiographs, if needed
- Oral photographs

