12.1 Funding Source

This study will be supported with product and cash payments by Zimmer Biomet. The bone graft procedure, the implant and the research procedures will be covered by the study. However, the two standard of care CBCT scans, implant crown and abutment will not be covered as part of this study.

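### The CBCT time point one year after implants has no scan, two years of follow-up after restoration cannot fit before month 24, Section 7.2 yields no volume result, and pre-implant scan timings conflict

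*Combined protocol and SAP*

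**What the plan says.** All references are to the combined protocol and SAP.

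- **Volume time points.** Section 3.3 follows bone volume on CBCT, "comparing it from the time of placement, 8 months post-grafting and one-year post implant insertion".
- **Scans planned.** Section 1.5 states "There will be 3 CBCT scans": one pre-operative, one immediately after grafting, and a last one. A limited scan is added if the second sinus is grafted at a later visit. On the last scan it says "The third scan is performed 8 months after the sinus augmentation surgery as per standard of care prior to implant placement".
- **Late visits.** Visits 8 and 9 (Sections 6.11 and 6.12, months 18 and 24) list "Standardized peri-apical radiographs, if needed" and no CBCT. Attachment A has no CBCT row beyond the pre-implant scan.
- **Follow-up.** The Study Summary says "subjects are followed for a period of two years after implants are restored". Section 1.1 gives the aim as to "follow the survival of the dental implants up to two years after prosthetic loading". The Protocol Summary sets participant duration at 24 months and study duration at 42 months. Section 6.9 places implants at month 8.
- **Volume measurement.** The Study Summary, Section 1.5 and Section 3.3 all promise a radiographic or CBCT volume comparison. Section 7.2 quantifies radiographs only as bone height at three sites per sinus, averaged. The primary objective in Section 2 lists graft volume among the outcomes obtained by histology; the secondary objective makes it radiographic.
- **Timing.** The pre-implant CBCT is at 8 months in Sections 1.5 and 3.3 and in Attachment A, at both 8 and 6 months within Section 3.1, and at month 7 ± 2 weeks in Section 6.8. Section 5.2 speaks of 6 months of follow-up before cores are harvested; Section 6.9 takes cores at month 8.

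**The concern.** A secondary endpoint names a measurement that the visit schedule never takes, and the Study Summary describes longer implant follow-up than any subject can have. If the text stands, the report must either leave one of three volume time points blank or explain its absence as a deviation, and readers may take the implant data as two-year results after restoration.

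Bone volume is in the trial's title. An analyst who follows Section 7.2 literally will produce heights and nothing that answers the volume question.

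The conflicting scan times leave open how old the graft is when the second volume reading is taken. Where the two sinuses are grafted on different days, the two grafts may also differ in age at a common scan or core date.

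**Working it through.** **Inputs.** Implant placement: month 8 ± 7 days (6.9). Visit 8: month 18 ± 7 days (6.11). Visit 9, the last: month 24 ± 7 days (6.12). Visit 5: month 7 ± 2 weeks (6.8). Second surgery, if staged: week 4 ± 7 days (6.5), no later than 6 weeks after the first (3.1, 6.3). Subjects: 10. One month is taken as 30.44 days, so 7 days = 0.23 month.

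**The plan's own figure.** The 24-month participant duration agrees with Visit 9 at month 24. It does not agree with implant placement plus two years after restoration, as step 2 shows.

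**1. The one-year scan**
- One year after placement: 8 + 12 = month 20 (19.8 to 20.2 with the Visit 6 window).
- Visit 8 is 9.5 to 10.5 months after placement: 18 − 8 = 10, ± 0.46 for the two windows.
- Visit 9 is 15.5 to 16.5 months after placement: 24 − 8 = 16, ± 0.46.
- No visit falls at one year, and neither late visit carries a CBCT. Of the three planned scans, and the extra one for staged surgery, none follows implant placement. The time point is empty in 10 of 10 subjects.

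**2. Follow-up after restoration**
- From placement: 24 − 8 = 16 months (15.5 to 16.5 with windows). This is the most available even if restoration were on the day of placement.
- No restoration visit is scheduled. Section 1.1 says "The process of osseointegration takes from 4-8 weeks, after which a dental prosthesis can be placed on the implants". Taking 4 to 8 weeks as the earliest interval is an assumption: 28/30.44 = 0.92 month and 56/30.44 = 1.84 months.
- Available: 16 − 0.92 = 15.1 months, or 16 − 1.84 = 14.2 months.
- Shortfall against 24 months: 8.9 to 9.8 months (8.0 with immediate restoration).
- Two years after restoration would end at month 8 + 24 = 32.0 at the earliest, or at months 32.9 to 33.8 under the assumption.

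**3. Volume**

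No arithmetic applies. Section 1.5 compares the immediate post-operative scan with the pre-implant scan for change in volume and loss of height. Section 7.2 carries only the height forward. No section says how volume is computed on the images, or how height would be converted to it.

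**4. Timing**
- The Visit 5 window runs from 6.5 to 7.5 months (7 ± 14/30.44), so it contains neither 6 nor 8 months.
- Staging does not remove the conflict. With the second sinus grafted at week 4, month 7 is 7 − 0.92 = 6.1 months after the second graft, but still 7 months after the first.
- For cores taken from both sinuses on one date, the staged age gap is 21 to 35 days by the Visit 4 window and up to 42 days by the 6-week limit.

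**The case against.** Several points on the other side are sound and limit what may be claimed.

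- **Volume is not wholly undefined.** The Study Summary and Section 1.5 state the scans, the comparison and a height measure. A reader might infer that method and rank are both open to choice after the data are seen. The rank is not: Sections 3.2, 3.3 and 7.2 and the secondary objective all keep volume out of the primary outcomes. One phrase in the primary objective is out of line. What stands is that 7.2 contains no volume computation.
- **The funding text proves little.** Section 12.1 says "the two standard of care CBCT scans, implant crown and abutment will not be covered as part of this study". That concerns payment for standard-of-care scans and does not show that no later research scan exists. The finding rests on Section 1.5, the visit lists and Attachment A. Attachment A also marks peri-apical films at Visits 8 and 9 with a plain X, whereas the visit text makes them conditional. Neither is a CBCT.
- **The study lasts 42 months.** A course of 32.0 to 33.8 months would leave 42 − 33.8 = 8.2 to 42 − 32.0 = 10.0 months for accrual, so longer follow-up could be accommodated. It would still need visits after month 24, and none is planned.
- **Section 1.1 sets a ceiling.** Its wording on follow-up after loading is a maximum, so the firm contradiction is the Study Summary against the 24-month participant duration.
- **Core timing is ambiguous.** Section 5.2 can be read as a period of follow-up before a month-8 harvest, not as a second harvest date.
- **Graft age has no sized effect.** A reader might infer that staged surgery damages the primary histology. The documents give no figure relating healing time to vital bone, same-visit surgery is preferred (6.2), and the number staged may be zero.

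**Conclusion.** The concern holds in four parts of unequal weight.

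1. The CBCT time point one year after implants cannot be observed in any of the 10 subjects under the current schedule. This needs no assumption.
2. The Study Summary's two years after restoration cannot be delivered. At most about 16 months from placement is available. The 14.2 to 15.1 months after restoration depends on the assumed 4 to 8 weeks. Implant survival to month 24 remains observable, so the documents do not support saying that survival cannot be assessed.
3. Section 7.2 as written produces heights but no volume result, although a volume comparison is promised elsewhere.
4. The pre-implant CBCT has three stated times, and the wording on the interval before core harvest is ambiguous. In staged subjects only, grafts may differ in age by up to 6 weeks at a common core date. No effect on the histology is claimed.

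Sample size, power and the primary histological comparison are not affected by parts 1 to 3. The point should be fixed before analysis, but it does not threaten the primary result.

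**What to change.** 1. **Section 3.3:** remove the time point one year after implants, leaving the immediate post-operative versus pre-implant comparison that Section 1.5 already describes. The downside is that no CBCT statement can be made after implant placement. Keeping the point would need an added research scan and attendance near month 20, between Visits 8 and 9: 10 scans, each with a CTDI of 6.61 mGy for the two-sided field given in Section 1.5. That is not a cheap change.
2. **Study Summary and Section 1.1:** reconcile the follow-up statements with the schedule. Under the current visits, state follow-up as to month 24, about 16 months after implant placement. A longer claim would require added visits.
3. **Section 7.2:** define graft volume on the scans already planned, as the pre-implant volume relative to the same sinus's immediate post-operative volume. Report the within-subject difference between grafts A and B with a 95% confidence interval, and keep mean height as supportive. Cost: 10 subjects × 2 sinuses × 2 scans = 40 image readings.
4. **Section 2:** correct the phrase in the primary objective that attributes volume to histology, so that volume is secondary and measured on CBCT, in line with Sections 3.2, 3.3 and 7.2.
5. **Timing:** reconcile Sections 1.5, 3.1, 3.3, 5.2, 6.8 and 6.9 and Attachment A; no timing is recommended here. Record each graft's age in days at scan and at core collection (2 sinuses × 2 occasions = four values per subject), and report the A−B age difference beside the results.

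Apart from the image readings and the graft-age entries, the changes are to wording. They need no new visits, scans or subjects.

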3.4 Primary Safety Endpoints

Not applicable. These products are already commercially available and FDA approved.

4 ADMISSION CRITERIA

4.1 Inclusion Criteria

1. Age - 25 to 65 years.
2. Good physical health
3. Capable of maintaining good oral hygiene

CONFIDENTIAL

This material is the property of the NYU College of Dentistry. Do not disclose or use except as authorized in writing by the study sponsor

4. Missing posterior maxillary teeth on both sides and less than 5mm of residual jaw bone requiring maxillary sinus augmentation prior to dental implant placement

5. Capable and willing to give informed consent

4.2 Exclusion Criteria

1. The presence of underlying medical conditions that may pose an undue risk for sinus surgery.
2. Patients with untreated oral infections.
3. Pregnant and lactating females.
4. Individuals who have the habit of smoking and/or tobacco chewing.
5. Patients not willing to participate in the study.

4.3 Subject Recruitment

Potential subjects are regular patients at NYUCD Department of Periodontics and Implant Dentistry and completing planned treatment. Subjects will be offered the opportunity to participate in a randomized, split mouth study comparing bone graft particle size. Written and verbal consent will be obtained. Patients/subjects will be free to 'opt out' of the study without consequence to their clinical care.

Both sizes of graft material that will be used for the study are also utilized by the clinicians for sinus augmentation procedures. To date there are no specific guidelines as to which particle size is more favorable and therefore should be exclusively used for the sinus augmentation procedures.

Bone core will be collected for research purposes during your implant surgery. These bone specimens are otherwise discarded. Personal identifying information will not be used in the analysis. Bone specimens will be coded and not identifiable by laboratory personnel or clinical investigators in this study. Only authorized study personnel will have access to the specimen-coding scheme, which will be kept in a locked file cabinet accessible only to the study investigators. No patient likenesses or personal identifying information will be used in publications or presentations.

4.4 Early Withdrawal of Subjects

4.4.1 When and How to Withdraw Subjects

Subjects will be monitored for satisfactory healing of the treated sites. If a subject has an adverse event resulting in bone graft failure, appropriate steps will be taken to resolve the clinical complication. Should a test bone graft sites be deemed a failure, the subject will be offered to repeat the procedure after an appropriate healing interval. In such cases, the subject will remain enrolled in the study until completion. If a subject elect to refuse further study participation, the subject will be terminated from the study and offered alternative standard treatment options. Upon withdrawal from the study, an additional participant will be recruited in order to maintain the necessary sample size.

4.4.2 Data Collection and Follow-up for Withdrawn Subjects

Subjects who fail to return for follow up appointments will be contacted by telephone up to three times. If telephone contact fails certified letter will be sent to the subjects last known mailing address. Every effort will be made to follow up with subjects until the subject is deemed lost to follow up.

5 Study device

5.1 Description

Bone graft material will consist of four to six grams of commercially available human donor bone allograft (Puros Allograft Bone Particles, Zimmer Biomet, Palm Beach Gardens, FL USA) consisting of cortical and cancellous bone chips of both 250-1000 microns, and 1000-2000 microns size, or 1000-2000 microns size alone. The method and composition of these products has been described, both products are FDA approved and commercially available. The harvesting and processing of the graft materials is briefly described as follows:

CONFIDENTIAL

This material is the property of the NYU College of Dentistry. Do not disclose or use except as authorized in writing by the study sponsor

Puros Allograft Bone Particles are sterile, dehydrated cortical and/or bone from donated human tissue. The donated human tissue utilized for this implant was recovered from a donor screened for risk factors associated with infectious diseases and medical conditions that rule out donation. The donor's blood was tested for relevant communicable diseases in a laboratory certified under the Clinical Laboratory Improvement Amendments of 1988 (CLIA) or equivalent and registered with the U.S. Food and Drug Administration (FDA) for donor testing. The following test criteria were met for this donor:

REQUIRED INFECTIOUS DISEASE TESTING BLOOD TEST ACCEPTABLE RESULT

- HIV-1 / HIV-2 Antibody Negative/ Non-Reactive
- Hepatitis C Virus Antibody Negative/ Non-Reactive
- Hepatitis B Surface Antigen Negative/ Non-Reactive
- Hepatitis B Core Antibody (Total) Negative/ Non-Reactive
- Syphilis Negative/ Non-Reactive
- Human T-Cell Lymphotropic Virus I/II Antibody Negative/ Non-Reactive
- HIV-1 NAT-TMA Negative/ Non-Reactive
- HCV NAT-TMA Negative/ Non-Reactive

A licensed physician for RTI Biologics Inc. determined that the donor met eligibility requirements. The physician utilized available relevant information which may have included, but was not limited to: family/next-of-kin interview, medical/hospital records, donor physical assessment, infectious disease test results, radiology/pathology reports, death certificate and autopsy report (if performed). Puros Allograft Bone Particles and the CopiOs Pericardium membrane are preserved by the Tutoplast® process which maintains the collagen matrix of native bone and undergoes 5 stages of: i. Delipidization, ii. Osmotic treatment, iii. Oxidative treatment, iv. Solvent dehydration, and v. Low dose gamma radiation is applied terminally to the product to achieve a sterility assurance level (SAL) of 10^{-6} .

5.2 Treatment Planning

4 to 6 grams of study material will be placed at the time of each sinus augmentation surgery as described in the clinical protocol. Subjects will be followed for a period of 6 months prior to harvesting of the bone graft cores prior to implant placement.

